7.3.2 Maximum stable gain

Measurement of microphone and accelerometer signal (spectrum and impulse response) in response to a stimulus generated by the implanted actuator, as defined in D1673818.

7.3.3 Audiometric thresholds

Bone conduction thresholds at audiometric frequencies from 250 to 6000 Hz, measured in accordance with clinical practice.

Direct thresholds (using the implant as a test signal generator), at audiometric frequencies from 250 to 6000 Hz, measured in accordance with clinical practice.

7.4 Safety Evaluations and Procedures

There will be a data safety monitor who will review all AEs, ADEs and DDs.

Safety endpoints will be a summary of AEs/ADEs and DDs from the screening to end of the last subject last visit.

7.4.1 Concomitant Medication and Therapies

Not applicable

7.5 Equipment Used for Evaluation of Performance and Safety

The annual calibration certificates of the audiometer, tympanometer and sound treated room for audiometric testing will be kept in the site resources file.

7.6 Sponsor Role in Conduct of the Clinical Investigation

Subject matter experts employed by the sponsor will perform the acoustic measurements on-site.

8 RISKS AND BENEFITS OF THE APPROVED MEDICAL DEVICE ON TEST AND CLINICAL INVESTIGATION

8.1 Anticipated Clinical Benefits

The anticipated clinical benefits of implantation of the AMDT prior to the start of the study are described in the Physician's Guides and not affected by the study.

The anticipated future clinical benefit of the data collection and analysis of the study is to provide optimized clinical guidance for patient selection based on level of hearing loss.

The study endpoints are expected to inform future designs of active middle ear implants with an implantable microphone.

8.2 Anticipated Adverse Device Effects

There are no anticipated adverse device effects related solely to this investigation.

8.3 Risks Associated with Participation in the Clinical Investigation

The clinical trial does not prescribe medical treatments. No interaction with medication that may be given as part of clinical routine is anticipated.

Theoretically, the stimulation of the patient's cochlea with the white noise signal used to measure maximum stable gain could damage residual hearing, if it was dangerously loud. The maximum stimulation level that can be set in the software is 85 dB MET (broadband), which is a -35 dBV drive level to the actuator (Jenkins, Pergola, & Kasic, 2007). Actuator efficiency as measured in temporal bone studies and clinically (Grossöhmichen et al., 2017) is below 120 dB SPLeq @ 1V median, so the -35 dBV corresponds to 85 dB SPLeq loudness perceived by the patient. Even at exceptionally good actuator efficiency of 125 dB SPLeq @ 1V, equivalent loudness will be below (125-35) = 90 dB SPLeq.

A stimulation level of 91 dB SPL is deemed safe for a maximum of 2 hours per day continuous exposure, it is the maximum acceptable loudness dosage for workplace noise hazards (NIOSH, 1998), below which an employer is not even required to offer hearing protection. The planned measurement duration (see below) is 2 conditions x 3 repetitions x 10s = 60s, far below the 2h limit.

8.4 Risk Mitigation

- The risk of acoustic overstimulation will be mitigated by limiting the stimulus level by design, as described above
- All reported ADEs and DDs will be regularly reviewed by the Sponsor's Clinical review Board for the duration of the study to facilitate early detection and appropriate intervention if events are unanticipated with respect to incidence, severity, or outcome.

8.5 Risk-to-Benefit Rationale

The software and hardware that will be used is CE marked, ensuring conformity with the relevant Medical Device Directive essential requirements. The clinical safety (risks) and benefit relevant to

the anticipated performance of the Carina system are documented in the respective Physician's Guides for these devices.

The findings from this clinical investigation will be important to providing optimized clinical guidance for patient selection based on level of hearing loss, and it will inform the design of future active middle ear implants with an implantable microphone.

9 STATISTICAL CONSIDERATIONS

9.1 General Considerations

There will be no formal statistical analyses given the absence of statistical null hypotheses in this pilot investigation.

Descriptive statistics will be used to summarise the endpoints; such as means, medians, standard deviations, confidence intervals and interquartile ranges.

9.2 Endpoints

1. Acoustic sensitivity of implanted microphone [dB FS for 0.1 Pa], in-situ, for audiometric frequencies 250-6000 Hz, median and percentiles
2. Ratio [dB] of response of implanted microphone to response of implanted accelerometer, in-situ, for audiometric frequencies 250-6000 Hz, median and percentiles
3. Transfer function from Carina output to actuator [dB FS] to Carina input from implanted microphone [dB FS], for audiometric frequencies 250-6000 Hz, with ear canal open and ear canal plugged
4. Identification of the system's acoustic and vibration transfer functions including non-linear components.

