4 BACKGROUND INFORMATION AND RATIONALE

4.1 Introduction and Study Rationale

The totally implanted Carina System is an active middle ear implant where all components (microphone, signal processing electronics, power source, and middle ear actuator) are implanted under the skin, making the system invisible and compatible with occupations and lifestyles that involve exposure to humidity or dust.

Placing a microphone under the skin affects its acoustic sensitivity and vibration sensitivity. With higher vibration sensitivity of the microphone, it may pick up small vibrations of the skull caused by the actuator coupled to a middle ear ossicles, which may lead to feedback squealing, similar to a conventional hearing where an acoustic feedback pathway from speaker to microphone may led to feedback squealing.

So far, acoustic sensitivity of an implanted microphone has been measured in bench and cadaver studies, and in a very small number of subjects implanted with a percutaneous access to the microphone (Gérard et al., 2017). Now, software is available to enable non-intrusive microphone measurements in existing patients with the Carina device, through a wireless link to the implant.

Detailed knowledge of the acoustic sensitivity of the implanted microphone, and its inter-individual variability, will allow more accurate calculation of overall system performance, and thereby more accurate prediction of clinical outcomes.

Detailed knowledge of the vibration sensitivity and the ratio of acoustic to vibration sensitivity will help to optimize future signal processing strategies intended to reduce the perception of body sounds, and the to reduce feedback.

Clinical studies on device performance typically report speech intelligibility scores and aided thresholds or functional gain, but it cannot be inferred to what extend the observed functional gain is determined by audiological needs, or the subject's preferences, or device limitations. With the research software available now, an objective measurement of the feedback transfer function and thereby of maximum stable gain can be made, which is independent of the audiological profile of the individual study subject, and their listening preferences.

Detailed knowledge of objectively measured maximum stable gain, and its inter-individual variability, will allow more accurate calculation of overall system performance, and thereby more accurate prediction of clinical outcomes.

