6 OBJECTIVES

6.1 Objectives

Since this study is a pilot investigation without powering to reject specific null hypotheses, objectives and associated endpoints in section 9.2 are listed without differentiation between primary and secondary objectives.

1. To characterize Carina microphone sensitivity, in-situ, and its variability
2. To characterize the ratio of (a) microphone response to sound to (b) accelerometer response to sound, in-situ, and its variability
3. To characterize Carina microphone impulse response for acoustic and actuator stimulation
4. To objectively measure maximum stable gain, i.e. gain before feedback squealing would occur

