7 DESIGN OF THE CLINICAL INVESTIGATION

7.1 General

The investigation is a single-centre, prospective, single-arm, post-market, non-interventional, pilot clinical investigation in adults previously implanted with the Carina system.

The subjects will include men and women aged 18 years and over.

Subjects will attend one scheduled study visit to be assessed as described in the CIP Schedule of Events (section 3). At the study visit, several objective acoustic measurements will be performed that do not require active participation from the subject. No data monitoring committee will be used for this clinical investigation.

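### Do separate summaries of microphone sensitivity and feedback transfer function, with no rule in section 9 for the three gain repeats, leave the stable-gain results inadequate?

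*Combined protocol and SAP*

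**What the plan says.** Section 6.1 states objective 4 as "To objectively measure maximum stable gain, i.e. gain before feedback squealing would occur". Section 9.2 serves it with endpoint 3, "Transfer function from Carina output to actuator [dB FS] to Carina input from implanted microphone [dB FS"], at the audiometric frequencies, "with ear canal open and ear canal plugged". Endpoint 1 is a separate quantity: "Acoustic sensitivity of implanted microphone [dB FS for 0.1 Pa], in-situ, for audiometric frequencies 250-6000 Hz, median and percentiles". Endpoint 4 covers the "acoustic and vibration transfer functions including non-linear components".

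Section 4.1 gives two of these quantities the same use. On sensitivity: "Detailed knowledge of the acoustic sensitivity of the implanted microphone, and its inter-individual variability, will allow more accurate calculation of overall system performance". On gain: "Detailed knowledge of objectively measured maximum stable gain, and its inter-individual variability, will allow more accurate calculation of overall system performance".

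Section 7.1 has one measurement occasion: "Subjects will attend one scheduled study visit". Sections 7.3.1 and 7.3.2 refer to document D1673818 for the measurement procedure; it is not among the documents supplied. Section 8.3 gives two conditions, three repetitions and 10 s each for the gain measurement. Section 9.1 rules out formal analyses and gives an open list of descriptive statistics. Section 9.3 states no hypotheses.

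**The concern.** Endpoint 3 runs from digital output to digital input and has no reference to sound pressure. To know how much gain a subject can use from incoming sound to actuator drive, one needs that subject's sensitivity as well. Section 4.1 says both quantities feed a calculation of overall system performance and stresses variability between individuals. A reader may therefore expect the distribution of the combination, and separate medians, percentiles or SDs cannot supply it.

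The repeats raise a second doubt. They appear only in the noise-exposure argument of section 8.3, so section 9 does not show whether the reported spread is between subjects, partly repeat error, or computed from pooled readings. A smaller doubt is that the thresholds in section 7.3.3 feed no stated endpoint.

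If these doubts held, a descriptive study of at most 20 people would misstate the variability it sets out to describe.

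**Working it through.** **The plan's own figure.** Section 8.3: 2 × 3 × 10 s = 60 s. This reproduces. There is no sample size calculation, power or error rate to check.

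**Does endpoint 3 answer objective 4?** Let F be the feedback transfer function in dB (actuator output to microphone input). The loop reaches its feedback limit when device gain plus F equals 0 dB, so maximum stable gain = -F. Then SD(-F) = SD(F), the median changes sign, and the percentiles are mirrored. Gain and its spread between subjects follow from endpoint 3 alone. Endpoint 3, unlike endpoints 1 and 2, does not name median and percentiles, but the list in section 9.1 covers it.

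**The combined quantity.** Let S be sensitivity in dB FS at 0.1 Pa, which is 20·log10(0.1/0.00002) = 74.0 dB SPL. Sound-referenced stable gain is S - 74 - F, and

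SD(S - F) = √(SD_S² + SD_F² - 2ρ·SD_S·SD_F),

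where ρ is the correlation of S and F across subjects. The documents give neither SDs nor ρ. Assume both SDs are 5 dB, so SD(S - F) = √(50 - 50ρ):

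| ρ (assumed) | SD(S - F), dB | Error if independence (7.07 dB) is assumed |
|---|---|---|
| -0.3 | 8.06 | -12% |
| 0 | 7.07 | 0 |
| 0.3 | 5.92 | +20% |
| 0.6 | 4.47 | +58% |
| 0.9 | 2.24 | +216% |

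The algebra is right. The last column, however, measures a step that section 9 does not take: nowhere does it combine the two summaries. Because S and F come from the same subject at the same visit, anyone wanting the combination subtracts one from the other per subject, and ρ need not be known.

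Nor would S - 74 - F be overall system performance. It stops at actuator drive. Section 8.3 shows that the level reaching the patient also depends on actuator efficiency, with a median below 120 and an exceptional value of 125 dB SPLeq at 1 V, figures 125 - 120 = 5 dB apart.

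**Repeats.** With r the ratio of within- to between-subject SD (assumed), averaging three readings inflates the between-subject SD by √(1 + r²/3) - 1:

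- r = 0.1: √1.0033 - 1 = 0.2%
- r = 0.6: √1.12 - 1 = 5.8%
- r = 1.0: √1.333 - 1 = 15.5%

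For comparison, the 95% confidence interval of an SD from 20 subjects without repeat error runs from 0.76 to 1.46 times the estimate. Inflation of up to 6% is small against that.

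**Thresholds.** Section 7.3.3 has them measured as in clinical practice. Sections 8.1 and 8.5 name guidance on patient selection by level of hearing loss as an aim, to which thresholds are plausibly relevant. No endpoint in section 9.2 uses them, so no planned result changes.

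**The case for a change.** The best case for the concern starts from the algebra, which does not depend on the assumed values: the spread of a difference cannot be recovered from two separate spreads. Section 4.1 assigns both quantities to one calculation. The 20 subjects are everyone implanted at the site (section 7.2.3) and withdrawals are not replaced (section 7.2.6), so every piece of joint information counts, and an open-canal combination would need no new measurement. On the repeats, section 7.1.1 itself calls the design repeated-measures, yet section 9 does not exclude treating 20 × 3 = 60 readings as independent. That would shrink the confidence interval of a mean to 0.68, 0.59 or 0.57 of its correct width at assumed intraclass correlations of 0.5, 0.8 or 0.9.

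Two things stand: the algebra, and the plain fact that section 9 does not mention repeats. Neither makes the plan wrong. Section 4.1 speaks of each quantity with its own variability and promises no reported distribution of the combination. The paired data remain available, and with no hypothesis or error rate to protect, prespecifying the combination would gain little. Pooling 60 readings is not proposed anywhere. The interest stated in section 4.1 is variability between individuals, so the natural reading is one value per subject, frequency and condition. The averaging rule may well be in D1673818; that cannot be confirmed here, but its absence from section 9 is missing detail, not a faulty method.

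**Conclusion.** The concern does not hold. Endpoint 3 delivers objective 4 as worded, with its spread. Sound-referenced stable gain is an additional quantity a reader might like, not one the plan undertakes to report, and it can be computed later from paired data. The -12% to +216% range rests on assumed 5 dB SDs and assumed correlations, and applies only to a calculation nobody plans.

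The effect of repeats is 0.2% to 6% at assumed SD ratios of 0.1 to 0.6. It reaches 15.5% only when repeat error equals the spread between subjects. This assumes the three same-visit readings are reduced to their mean, which is what an analyst would sensibly do. The purpose of the thresholds is likewise a matter of detail. No decision rule, error rate or subject risk depends on any of these points.

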9.2.1 Exploratory Endpoints

Not applicable

9.3 Hypotheses

No formal testable hypotheses are applicable in this pilot study.

9.4 Sample Size Determination

No sample size has been calculated given the pilot nature of the investigation (see section 7.23). Up to 20 subjects will be enrolled in this study.

9.5 Analysis Populations

Given that the study is single arm with no formal statistical analyses, there is no clear need to impute missing data. The descriptive statistical analyses will be computed with the per protocol data set.

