7.2.6 Criteria for Subject Withdrawal

Subjects can decide to withdraw from the investigation at any time. The Investigator shall ask the reason(s), although the subject does not have to give a reason. If a reason for withdrawal is offered, it should be documented in the subject's source files and the case report form (CRF).

The Investigator or Sponsor may also decide to withdraw a subject from the clinical investigation if it is considered to be in their best interests.

Subject withdrawal may be for any of the following reasons:

- Adverse Event (AE)
- Device Deficiency (DD)
- CIP or GCP deviation
- Subject lost to follow-up
- Subject withdrew consent
- Subject death
- Sponsor decision
- Investigator decision
- Other (specify)

If a subject is lost to follow-up, every possible effort must be made by the study site personnel to contact the subject and determine the reason for discontinuation. It must be remembered however that the subject does not need to provide a reason/s. At least 3 separate attempts taken to contact the subject must be documented.

Enrolled subjects who are withdrawn/discontinued will not be replaced.

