9.9 Safety Analyses

The number and percent of patients with adverse events will be reported and tabulated. Adverse events will be summarized by event type, severity, seriousness, as well as relatedness to the device and implant procedure

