13 DEVIATIONS FROM THE CLINICAL INVESTIGATION PLAN

The Investigator(s) must not deviate from the CIP, except in case of an emergency to protect the safety and well-being of the subject(s). Such deviations will be documented by the site personnel in the source documentation for the subject and reported to the relevant EC as per institutional requirements and to the Sponsor as soon as possible from the date of the emergency.

If there is a deviation from CIP-defined assessments or parts thereof are omitted or completed incorrectly, the deviation will also be documented by the site personnel in the source documentation for the subject. Depending on the type or severity of the deviation the Investigator may be required to notify the EC, particularly if the deviation potentially impacts subject safety, performance of AMDT, or data integrity.

All CIP deviations will be documented in the eCRF to enable analysis and reporting by the Sponsor in the Clinical Investigation Report (CIR), or to the relevant regulatory authority(s), if applicable.

Gross misconduct on behalf of an Investigator, such as intentional non-compliance with CIP or GCP requirements or fraud, will result in disqualification of the Principal Investigator and/or Investigational Site from participation in the investigation. Data provided by the Principal Investigator or Investigational Site will be excluded from the per-protocol analysis group.

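### Does the undefined per-protocol set in section 9.5, with no denominator for adverse events in section 9.9, need a change to the plan?

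*Combined protocol and SAP*

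**What the plan says.** Section 9.5 is the only place that assigns an analysis set: "The descriptive statistical analyses will be computed with the per protocol data set". It adds that "there is no clear need to impute missing data". The per-protocol group is mentioned once more, in section 13, for gross misconduct by an investigator: "Data provided by the Principal Investigator or Investigational Site will be excluded from the per-protocol analysis group". For ordinary lapses, section 13 requires only a record: "If there is a deviation from CIP-defined assessments or parts thereof are omitted or completed incorrectly, the deviation will also be documented".

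On safety, section 9.9 says "The number and percent of patients with adverse events will be reported and tabulated", with no population named. Section 7.4 defines the safety endpoints as a summary of AEs, adverse device effects and device deficiencies, running from screening to the last subject's last visit. Section 11.2 has all AEs recorded from screening.

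Section 7.2.6 introduces its list with "Subject withdrawal may be for any of the following reasons". The list includes an AE, a device deficiency and "CIP or GCP deviation". It also says "Enrolled subjects who are withdrawn/discontinued will not be replaced". Section 14 defines the CRF statuses Consented, Screen Fail, Enrolled, Withdrawn and Complete, ties none of them to an analysis set, and allows withdrawn subjects to stay in safety follow-up.

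**The concern.** A per-protocol set with no membership rule leaves the analyst to decide who is in it, possibly after seeing the data. The one written exclusion does not help: at a single site, the misconduct rule removes everyone or no one.

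The AE table looks the more exposed. Per protocol is the only set named, and some withdrawal reasons are the very events section 9.9 counts. If the table were run on a set without withdrawn subjects, those with events could be the ones missing. AEs are also recorded before a subject reaches Enrolled status, so an event in a screen failure has no stated place.

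For performance, a strict no-deviation reading could discard a good microphone measurement because a bone conduction audiogram or direct threshold was missed, although no endpoint in section 9.2 uses either. With up to 20 subjects and no replacement, each exclusion is visible in the results.

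**Working it through.** The plan states no calculated figure here: the limit of 20 is the number of patients implanted at the site (section 7.2.3). The check is therefore how far the gaps could move a result, and whether the text leads there. The documents give no AE, withdrawal or omission rates, so all rates below are assumptions.

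**1. AE percentage: k/n with exact (Clopper-Pearson) 95% intervals.**

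| Enrolled | Those left out had AEs | Those left out had no AE |
|---|---|---|
| 1/20 = 5.0% (0.1–24.9) | 0/19 = 0% (0–17.6) | 1/19 = 5.3% (0.1–26.0) |
| 2/20 = 10% (1.2–31.7) | 0/18 = 0% (0–18.5) | 2/18 = 11.1% (1.4–34.7) |

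The middle column is the worrying one. It needs four things together:
- An AE occurs.
- The subject is withdrawn for it.
- Withdrawal removes the subject from per protocol.
- The AE table is run on per protocol.

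Section 7.2.6 makes the second possible, not automatic. No section supplies the third or fourth. Sections 9.6 and 9.7 refer back to section 9.1, whereas section 9.9 stands alone and refers to neither 9.1 nor 9.5. Section 7.4 sets a window with no compliance condition, and section 11.4 has all AEs reported in the CRF. Exposure is short: one visit, with participation of 1 day in the synopsis or 1 month in section 7.2.5. Section 8.2 anticipates no device effects arising solely from the study.

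Screen failures should be rare. Eligibility is adult age, being a current recipient, and willingness and ability to comply, in patients already implanted at the site.

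**2. Subjects kept for performance.** Take four blocks: audiogram, direct thresholds, microphone sensitivity with impulse response, and maximum stable gain. Let each be independently incomplete with probability p = 0.02 to 0.05.
- Strict no-deviation set, 20(1−p)^4: 20 × 0.98^4 = 18.4; 20 × 0.95^4 = 16.3.
- All available data per measurement, 20(1−p): 19.6; 19.0.
- Usable microphone data lost only through a missed threshold test, 20(1−p)[1−(1−p)²]: 19.6 × 0.0396 = 0.78; 19.0 × 0.0975 = 1.85.

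The loss is smaller if omissions fall on the same subjects. It arises only under the strict reading, which the text does not direct. Section 13 merely documents an omission, and declining to impute suggests that subjects with gaps stay in.

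**3. Effect on percentiles.** In 200,000 simulated samples of n = 20 from N(0,1), the 10th percentile has mean −1.157 and sampling SD 0.348. Two subjects are then excluded by a score correlated r with the value:

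| r | 10th percentile | Shift |
|---|---|---|
| +0.3 | −1.080 | 0.077 |
| +0.5 | −1.017 | 0.140 |
| −0.3 | −1.191 | −0.034 |
| −0.5 | −1.205 | −0.048 |

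The largest shift is 0.140/0.348 = 0.40 of the sampling SD. Section 9.2 asks for the median and unspecified percentiles. For the median, r = 0.5 gives a shift of about 0.09 SD against a sampling SD of about 0.27. Exclusion unrelated to the value moves the 10th percentile by about 0.007 SD.

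**The case for a change.** The best case for acting is that a route to a per-protocol AE table can be built from the text. Section 7.4 calls the AE summary safety endpoints, section 9.1 says descriptive statistics summarise the endpoints, and section 9.5 computes descriptive analyses on per protocol. On that reading, section 9.5 names a set other than all subjects, so one cannot simply assume everyone is counted. Section 14 lets withdrawn subjects stay in safety follow-up without saying whether their events are tabulated. A short clarification would need no extra data collection.

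The omissions stand, and so does the arithmetic. The inference is weaker. Section 9.2, under the heading Endpoints, lists only four acoustic measures, and safety has its own analysis section with no link to 9.5. Following withdrawn subjects for safety makes little sense if their events are then dropped. Even on the combined reading, a further rule would be needed to exclude a subject with an AE, and none is written. Late discretion is also constrained: section 13 has every deviation entered in the eCRF for the investigation report, and section 14 has each subject's status captured. As for measurement validity, sections 7.3.1 and 7.3.2 refer to D1673818, which is not among the documents, so one cannot say that criteria are absent.

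**Conclusion.** No change to the plan follows. Per-protocol membership and the AE denominator are undefined, but this is missing detail that a competent analyst fills sensibly: all recorded AEs tabulated, including those in withdrawn subjects, and each acoustic endpoint summarised on its valid measurements. No rule in the plan is shown to give a wrong result, and abandoning per protocol for the acoustic endpoints is not shown to be better.

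The extreme figures (10% becoming 0%, a 0.14 SD shift) are assumed worst cases. The first needs exclusion rules the plan lacks. The second pairs a tail percentile with the strongest correlation tried, and is still below half of that percentile's sampling SD. There is no test, error rate or power to protect, and at n = 20 the exact interval for one event already runs from 0.1% to 24.9%.

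The conclusion rests on section 9.5 being read as governing performance summaries, on AEs and withdrawals being few in a one-visit measurement study, and on deviations being recorded as section 13 requires.
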